## 4.4. Exploratory Endpoints Analysis

### 4.4.1. Definition of Endpoints

For the following endpoints, refer to previous sections for details.

PASI (section 4.2.1.1), IGA (section 4.2.1.2), DLQI/CDLQI (section 4.3.2.1.3), PSSD (section 4.3.1.1.3), mNAPSI (section 4.3.2.1.7), PROMIS-29 (section 4.3.2.1.8), and PROMIS-25 (section 4.3.2.1.9).

#### 4.4.1.1. Scalp Specific Investigator Global Assessment

Refer to section 4.3.1.1.4 for details.

Meeting ss-IGA score of 0 criteria: defined as achieving an ss-IGA score of absence of disease (0).

#### 4.4.1.2. Fingernail Physician's Global Assessment

Refer to section 4.3.2.1.10 for details.

Meeting f-PGA score of 0 criteria: defined as having an f-PGA score of clear (0).

#### 4.4.1.3. Physician's Global Assessment of Hands and/or Feet

Refer to section 4.3.2.1.11 for details.

Meeting hf-PGA score of 0 criteria: defined as having an hf-PGA score of clear (0).

#### 4.4.1.4. Static Physician's Global Assessment of Genitalia

Refer to section 4.3.2.1.6 for details.

Meeting sPGA-G score of 0 criteria: having an sPGA-G score of clear (0).

#### 4.4.1.5. Physician Global Assessment of Disease Activity

The PGA of Disease Activity is a 100 mm VAS and will be utilized for adolescent participants with a diagnosis of PsA at or before screening. Physicians are to complete the VAS to assess the participant's current arthritis activity. The anchors of the scale are "no arthritis activity" to "extremely active arthritis." Lower scores indicate less disease activity. The process for including this measure (PGA of disease activity) in the core set of variables for the assessment of JIA improvement has been captured in the literature.

#### 4.4.1.6. Participant Assessment of Psoriatic Arthritis Pain

This self-administered item is designed to assess the participant's reported pain associated with PsA over the past week on a VAS ranging from 0 (no pain) to 100 (worst possible pain). This assessment will be administered only to adult and adolescent participants who report having PsA at or before Week 0.

#### **4.4.1.7. Participant Assessment of Psoriatic Arthritis Disease Activity**

This self-administered item is designed to assess the participant's overall well-being over the past week on a VAS ranging from 0 (very poor) to 100 (very well). This assessment will be administered only to adult and adolescent participants who report having PsA at or before Week 0.

#### **4.4.1.8. Participant Assessment of Acceptability and Palatability**

Adolescent participants will be asked to provide responses to questions designed to assess the acceptability and palatability of the study drug.

#### **4.4.1.9. Genital Psoriasis Sexual Frequency Questionnaire**

Refer to section 4.3.2.1.12 for details.

Meeting GenPs-SFQ item 2 score 0 criteria: defined as having an GenPs-SFQ item 2 score of 0.

### **4.4.2. Analysis Methods**

In general, the efficacy analyses for exploratory endpoints will be based on FAS or randomized at Week 24 analysis set (Section 4.1). Simple descriptive summary statistics, such as n, mean, SD, median, interquartile range, minimum, and maximum for continuous variables, and counts and percentages for discrete variables will be summarized by study intervention group.

Unless otherwise specified, the treatment comparisons will be performed using the same analysis methods described in Section 4.3.2.3 for other secondary endpoints. The analysis strategy for ICEs and missing data will be handled in the same manner as other secondary analyses (section 4.3.2.3). No adjustments for multiple comparisons will be made for exploratory endpoints.

Additionally, graphical data displays may also be used to summarize the over time data if applicable.

#### **4.4.2.1. Analyses Through Week 24**

Efficacy analyses at Week 16 and over time through Week 24 will be summarized by randomized treatment group at Week 0.

- **Placebo:** participants randomized to the placebo group at Week 0

For over time summaries at Week 20 and Week 24, only participants who crossed over to receive JNJ-77242113 treatment will be included in the placebo cross over group.

- **JNJ-77242113:** participants randomized to the JNJ-77242113 treatment group at Week 0

#### **4.4.2.2. Analyses From Week 24 Through Week 52 – Randomized Withdrawal and Retreatment Period**

##### **Randomized Withdrawal Period**

To evaluate the maintenance of efficacy of JNJ-77242113 compared with treatment withdrawal

during the randomized withdrawal period, efficacy analyses at Week 52 and from Week 24 through Week 52 (withdrawal and retreatment period) will be summarized among adult participants who were rerandomized at Week 24.

- **Placebo (withdrawal group):** participants rerandomized to the placebo group at Week 24
- **JNJ-77242113:** participants rerandomized to the JNJ-77242113 treatment group at Week 24

Participants experiencing ICEs 1, 2 and/or 4 between Week 24 and Week 52 will be handled in the same manner as the other secondary analyses (section 4.3.2.3).

#### **Retreatment period**

To evaluate the efficacy of retreatment after relapse with JNJ-77242113, efficacy data at and after retreatment relative to the time of retreatment (i.e., at the time of retreatment, 4 weeks after retreatment, 8 weeks after retreatment) will be summarized for adult participants who were randomized to placebo at Week 24, were withdrawn from study agent at Week 24, experienced a loss of at least 50% of the Week 24 PASI improvement, and were retreated with JNJ-77242113. Selected endpoints will be summarized at scheduled visits after retreatment.

Participants experiencing ICEs 1-3 after retreatment will be handled in the same manner as the other secondary analyses (section 4.3.2.3) regardless of ICEs occurred prior to retreatment.

#### **4.4.2.3. Analyses Through Week 52 – Non-randomized JNJ-77242113 Treatment**

For participants who were not randomized at Week 24, efficacy data will be summarized over time from Week 24 through Week 52 in following treatment groups.

- **Placebo-> JNJ-77242113 (adults and adolescents):** participants randomized to placebo group at Week 0 and crossed over to receive JNJ-77242113 at or after Week 16
- **JNJ-77242113 (adult non-responders):** adult participants randomized to JNJ-77242113 treatment group at Week 0 who were both PASI 75 and IGA 0 or 1 non-responders at Week 24, and did not undergo randomization at Week 24

To evaluate efficacy of JNJ-77242113 in adolescent participants, efficacy data will be summarized from Week 0 through Week 52.

- **JNJ-77242113 (adolescents):** adolescent participants randomized to JNJ-77242113 treatment group at Week 0.

#### **4.4.2.4. Analyses From Week 64 Through Week 156**

The efficacy analyses from Week 64 through Week 156 will be performed for participants randomized to JNJ-77242113 at Week 0, or participants randomized to placebo at Week 0 and crossed over to receive JNJ-77242113 at or after Week 16 based on following data handling rules for ICE and missing data.

- Modified Non-Responder Imputation (mNRI) for binary endpoints: participants with ICE 1 will be considered as non-responders from that point forward. After accounting for ICE 1, missing data will be imputed using the same multiple imputations (MI) method specified in Section 4.2.3.2.1 for sensitivity analysis 1.
- Observed Cases (OC) for binary endpoints: selected endpoints (e.g., PASI responses, and IGA responses) will be summarized based on the observed data. No ICE rules will be applied, and missing data will not be imputed.
- MMRM model for continuous endpoints: participants with ICE 1 will be considered as zero change or zero percent change from baseline from that point forward. Missing data will be accounted for through correlation of repeated measures in the MMRM model.

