7. DISCONTINUATION OF STUDY INTERVENTION AND PARTICIPANT DISCONTINUATION

7.1. Discontinuation of Study Intervention

If a participant discontinues study intervention for any reason before the end of the study, then the Early Termination Visit assessments must be obtained (Section 1.3.2). Study intervention assigned to the participant who discontinued study intervention may not be assigned to another participant (Section 6.2). Additional participants will not be entered in this study. Participants who discontinue

study intervention but do not terminate study participation will continue to return for protocol-specified procedures and evaluations. Discontinuation from study intervention does not mean that the participant is required to withdraw informed consent and leave the study.

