**From Week 64 Through Week 156**

- The change and percent change from baseline in PASI total score will be summarized over time.
- The proportion of PASI responses (PASI 75, 90, and 100) will be summarized over time based on mNRI and observed data after accounting for ICE 1.

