#### **Phototherapy or Systemic Therapy**

The use of phototherapy or systemic medications that could affect psoriasis evaluations is not permitted at any time during the study.

These medications include:

- those targeted for reducing TNF $\alpha$  (including but not limited to adalimumab, infliximab, or etanercept).

- drugs targeted for reducing IL-12/23, IL17, or IL-23 (including but not limited to ustekinumab, briakinumab, guselkumab, tildrakizumab, secukinumab, risankizumab, ixekizumab, or brodalumab).
- alpha-4 integrin antagonists (including but not limited to natalizumab).
- JAK inhibitors (including but not limited to TYK2 inhibitors).
- PDE4 inhibitors (including but not limited to apremilast).
- oral and injectable (IV, intramuscular, or intralesional) corticosteroids.
- any other conventional systemic therapies that could affect psoriasis evaluations (including but not limited to methotrexate, cyclosporine A, acitretin, or other retinoids).
- antimalarial agents.
- herbal treatments.
- traditional Taiwanese, Korean, or Chinese medicines.

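### Exploratory Week 64 to 156 analyses handle only ICE 1, so PASI and IGA values observed on still-prohibited systemic, biologic or phototherapy treatment can count as JNJ-77242113 response

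*SAP*

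**What the plan says.** SAP 4.4.2.4 sets its own rules for Week 64 to Week 156. They cover participants randomized to JNJ-77242113 and placebo participants who crossed over to it.

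- **Binary endpoints, mNRI:** "participants with ICE 1 will be considered as non-responders from that point forward". Then: "After accounting for ICE 1, missing data will be imputed using the same multiple imputations (MI) method" that serves the first co-primary sensitivity analysis.
- **Binary endpoints, observed cases:** "No ICE rules will be applied, and missing data will not be imputed".
- **Continuous endpoints, MMRM:** "participants with ICE 1 will be considered as zero change or zero percent change from baseline from that point forward".

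For the same period, SAP 4.4.2.5 (PASI) and 4.4.2.6 (IGA) both describe response summaries "based on mNRI and observed data after accounting for ICE 1".

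Appendix 7 (SAP 6.7) defines ICE 2 in four parts: topical therapies for psoriasis with narrow exceptions, systemic corticosteroids for psoriasis, other systemic or biologic anti-psoriatic therapy, and phototherapy. The same appendix, like Protocol 6.9, permits most topicals after Week 52. It keeps topical JAK inhibitors and ultra-high potency corticosteroids prohibited, and for the rest it says: "The use of phototherapy or systemic medications that could affect psoriasis evaluations is not permitted at any time during the study".

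Protocol 7.1 says that participants who stop study intervention "but do not terminate study participation will continue to return for" scheduled evaluations. Protocol 1.3.2 schedules PASI and IGA at every visit from Week 64 to Week 156.

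**The concern.** The period has no concurrent control, so the intercurrent event rule is the main safeguard for attributing response to the study drug. ICE 2 drops out of that rule, yet part of what ICE 2 covers is still prohibited and can clear psoriasis by itself. The SAP gives no reason and has no other analysis rule for such therapy.

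Weeks 64 to 156 span 92 of the 156 treatment weeks and supply the only planned efficacy estimates beyond Week 52. Long-term maintenance rates could therefore include response produced by another effective drug. A curve drawn across Week 52 and Week 64 could also rise simply because the rule changed. Values recorded on the other therapy also enter the imputation and MMRM models, so they can influence what is inferred for participants with missing data.

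**Working it through.** The plan states no expected ICE 2 rate and no response rate for Week 64 to 156, so there is no figure to reproduce. The check compares the rules by period, traces who escapes them, and then sizes the effect under assumptions.

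**1. Handling of ICE 2 by period**

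| Analysis | SAP section | ICE 2 handling |
|---|---|---|
| Co-primary, Week 16 | 4.2.2.1.1, 4.2.3.1 | Composite: non-responder |
| Key secondary binary, to Week 52 | 4.3.1.3.1 | Composite: non-responder |
| Other secondary continuous | 4.3.2.3 | Composite: zero change |
| Exploratory, general rule | 4.4.2 | As other secondary, so composite |
| Exploratory, after retreatment | 4.4.2.2 | As other secondary, so composite |
| Exploratory, Week 64 to 156 | 4.4.2.4 | Not mentioned |

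Exploratory status does not explain the omission, because the other exploratory analyses keep ICE 2. The specific rule in 4.4.2.4 displaces the general one in 4.4.2.

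**2. Who is and is not caught from Week 64 under mNRI and MMRM**

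- Stops for lack of efficacy or an AE of worsening psoriasis, then starts a biologic: ICE 1 applies, giving non-response or zero change. Caught.
- Starts a prohibited systemic agent and stays on study drug: no rule applies. This is possible because Protocol 7.1.3 leaves discontinuation in that case to the medical monitor's discretion. Not caught.
- Is taken off study drug because prohibited therapy was started: that recorded reason is not an ICE 1 reason. Not caught.
- Stops for an unrelated reason, starts a biologic and keeps attending: not caught.

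Example: a participant re-randomized at Week 24 starts a biologic at Week 50 without ICE 1. The participant is a non-responder at Week 52 under 4.3.1.3.1 and can be a responder at Week 64 under 4.4.2.4.

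**3. Size**

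Let f be the share starting still-prohibited therapy, e the fraction of those already non-responders through ICE 1, and r the response rate on that therapy. The mNRI response rate exceeds the rate under a retained composite rule by

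f × (1 − e) × r.

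All three inputs are assumptions: f 1% to 10%, e 0% to 50%, r 50% to 90%. The counts use the target of 600 participants as an upper bound for the denominator.

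- Low: 0.01 × (1 − 0.5) × 0.5 = 0.0025, or 0.25 points (600 × 0.0025 = 1.5 participants).
- Middle: 0.05 × (1 − 0) × 0.7 = 0.035, or 3.5 points (21 participants).
- High: 0.10 × (1 − 0) × 0.9 = 0.09, or 9 points (54 participants).

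**4. Observed cases**

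Section 4.4.2.4 applies no intercurrent event rule to observed cases. Sections 4.4.2.5 and 4.4.2.6 can be read as applying ICE 1 to them. The phrase may be meant to qualify mNRI only, but two programmers could produce different tables.

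**The case against.** The strongest reply is that little depends on this rule. The analyses are exploratory and open-label, no hypothesis test uses them, and the objectives tables name no endpoint after Week 52. That stands, and it limits the point's importance.

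A second reply is that counting observed values whatever other therapy is taken is a legitimate treatment-policy estimand. Someone who stops while responding and later takes a biologic would be scored as a failure under a composite rule. That is fair, and it means the overstatement is measured against the composite strategy. But the SAP does not declare a treatment-policy choice for this period, and composite is its own strategy for this event everywhere else.

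A third reply is that ICE 2 had to go because most topicals become permitted. This is a plausible motive, though unstated, and it explains only the topical part.

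Use of disallowed treatment would also be visible in the protocol deviation and concomitant medication summaries (SAP 6.3 and 6.4). That helps a reader but does not alter the response rates.

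A reader might infer that every response obtained on prohibited therapy is credited to JNJ-77242113. The documents do not support that for mNRI or MMRM, since ICE 1 removes those who first stopped for lack of efficacy or worsening psoriasis.

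**Conclusion.** The point holds for a defined group: participants who start a still-prohibited therapy while on study drug, or after stopping for a reason other than ICE 1, and whose later PASI or IGA values are collected. As written, SAP 4.4.2.4 counts those values as JNJ-77242113 response.

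The overstatement is about 0.25 to 9 percentage points. That range rests wholly on assumed use, response and ICE 1 overlap. It also presumes continued attendance, which Protocol 7.1 provides for but does not quantify. The documents do not support a claim that the inflation is known to be several points, nor that it reaches the trial's main conclusions, since ICE 2 is handled in the co-primary, key secondary and Week 52 analyses. The correction is worth making because these would be the reported long-term efficacy rates. The observed-case wording is a separate, minor inconsistency.

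**What to change.** In SAP 4.4.2.4, keep the composite strategy (non-response under mNRI, zero change under MMRM) for a restricted ICE 2. Limit it to therapies the documents still prohibit after Week 52: systemic and biologic agents, phototherapy, ultra-high potency topical corticosteroids and topical JAK inhibitors. State how such therapy begun before Week 52 carries forward, and report the number of participants affected at each visit.

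The existing ICE 2 flag cannot be reused unchanged, because the first item of the Appendix 7 list counts topicals that become permitted after Week 52. That item needs narrowing, which requires the potency class of topical corticosteroids; the other three items can stand.

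Separately, make 4.4.2.4 agree with 4.4.2.5 and 4.4.2.6 on whether ICE 1 applies to observed cases.

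The cost is a SAP wording change, one modified derivation and somewhat lower long-term response rates. No new data collection is needed beyond the concomitant therapy already recorded. If the sponsor does intend a treatment-policy strategy here, it should say so, justify it and report the same counts.

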##### **4.2.3.2.1. Sensitivity Analysis 1**

Under the co-primary estimands, a sensitivity analysis using multiple imputation will be performed for each co-primary endpoint. After accounting for the ICEs, missing data will be imputed using multiple imputations (MI) by fully conditional specification (FCS).

More specifically, the missing PASI 90 response and IGA 0 or 1 response will be imputed with FCS logistic regression including treatment group, baseline PASI score or IGA score, PASI 90 response or IGA 0 or 1 response status through Week 16, age group, baseline weight category for adults, and geographic region in the model with seed = 789 and 500 imputations.

A CMH test stratified by age group, baseline weight category for adults, and geographic region will be used to obtain the CMH statistic for each imputed dataset.

The general association test statistic from the CMH test for each imputed dataset will be transformed using the Wilson-Hilferty transformation ([Wilson and Hilferty, 1931](#)) to create a more normal distributed statistic:

$$Z = \frac{(CMH)^{(1/3)} - 7/9}{(2/9)^{(1/2)}}.$$

The resulting transformed values will be combined using SAS PROC MIANALYZE to obtain an overall p-value for the CMH test.

The common risk differences and 95% CIs in co-primary endpoints will be calculated using Mantel-Haenszel stratum weights and Sato variance estimator ([Sato, 1989](#)) adjusting for age group, baseline weight category for adults, and geographic region for each imputed dataset. The resulting values will be combined to obtain an overall risk difference and 95% CI.

#### 4.2.3.2.2. Sensitivity Analysis 2

Under the co-primary estimands, another sensitivity analysis will be performed using a tipping point analysis with Bernoulli draws to impute missing PASI 90 and IGA 0 or 1 response status at Week 16 after ICEs are accounted for. The tipping point analysis involves the following distinct steps:

1. Some p will be assumed for each treatment group's response rate, which could vary by treatment group, to impute the response status (Yes/No) for participants with a missing response based on a Bernoulli distribution. This will be repeated 200 times with seed = 20240719 to generate 200 multiple imputations.

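### The imputation model for Week 64–156 responder rates is borrowed from the Week 16 sensitivity analysis without being adapted, so later loss of response may be left out

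*SAP*

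**What the plan says.** SAP 4.4.2.4 handles binary endpoints from Week 64 to Week 156 in two steps. First, "participants with ICE 1 will be considered as non-responders from that point forward". Then "missing data will be imputed using the same multiple imputations (MI) method specified in Section 4.2.3.2.1 for sensitivity analysis 1".

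The section referred to, SAP 4.2.3.2.1, is a sensitivity analysis of the co-primary endpoints at Week 16. There, "the missing PASI 90 response and IGA 0 or 1 response will be imputed with FCS logistic regression including treatment group". The other predictors are baseline PASI or IGA score and "PASI 90 response or IGA 0 or 1 response status through Week 16, age group, baseline weight category for adults, and geographic region", and the settings are given as "in the model with seed = 789 and 500 imputations". No later visit is named, and neither is the Week 24 re-randomisation.

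For the observed-case companion analysis, SAP 4.4.2.4 says "No ICE rules will be applied, and missing data will not be imputed". The Week 64–156 paragraphs of SAP 4.4.2.5 (PASI) and 4.4.2.6 (IGA) instead describe summaries "based on mNRI and observed data after accounting for ICE 1".

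**The concern.** Imputing under missing at random is credible here only if the model conditions on what was last known about the participant. The schedule in Protocol 1.3.2 collects PASI and IGA at all nine visits from Week 64 to Week 156. The borrowed model, taken at its word, uses none of them, and nothing from Weeks 20 to 52 either. Three features of this period make the mismatch worse:

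- By Week 64 everyone still on treatment is assigned JNJ-77242113 (SAP 1.2), so the Week 0 arm no longer describes treatment. Continuation, withdrawal with retreatment, and not being re-randomised are not distinguished.
- For participants who crossed over from placebo, all response history through Week 16 was recorded on placebo.
- The model is written for two endpoints. The long-term binary summaries also include PASI 75, PASI 100 and IGA 0 (4.4.2.5, 4.4.2.6), PSSD scores of 0 and the itch response (4.4.2.13), and DLQI/CDLQI 0 or 1 (4.4.2.14).

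What is at stake is the accuracy of the published long-term response rates, and whether two programmers following the SAP would get the same ones.

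**Working it through.** The documents give no response rate, dropout rate or ICE 1 share for Weeks 64–156, so there is no planned figure to reproduce. The size below is an illustration on stated assumptions.

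**Inputs.** From the documents: 59% PASI 90 at Week 16 on active (SAP Section 5); the ICE 1 rule (4.4.2.4); the predictor list (4.2.3.2.1). Assumed: probability of response at the last visit before the target is 0.85 for a Week 16 responder and 0.50 for a non-responder; probability of response at the target visit is 0.90 if the last status was response and 0.15 if not.

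**Formulas.** R is Week 16 status, L the last status, d_L the dropout probability, and e the share of dropouts with L=0 who are ICE 1.

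- Observed mass: O_RL = P(R,L)(1−d_L).
- ICE 1 mass: I_R0 = P(R,0)·d_0·e, and I_R1 = 0. It counts as non-response, is not imputed, but is in the data that the model is fitted to.
- Missing mass: M_RL = P(R,L)·d_L − I_RL.
- True composite rate: T = Σ(O_RL + M_RL)·P(Y=1|L).
- Imputed probability from Week 16 status only: q_R = Σ_L O_RL·P(Y=1|L) / Σ_L(O_RL + I_RL).
- Estimate: E = ΣO_RL·P(Y=1|L) + Σ_R M_R·q_R, where M_R = Σ_L M_RL. Bias = E − T.

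**Worked case: dropout 10% of current responders, 30% of current non-responders, no ICE 1.**

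- P(L=1) = 0.59×0.85 + 0.41×0.50 = 0.7065, so T = 0.7065×0.90 + 0.2935×0.15 = 0.6799.
- q for Week 16 responders = (0.45135×0.90 + 0.06195×0.15)/0.5133 = 0.8095.
- q for Week 16 non-responders = (0.1845×0.90 + 0.1435×0.15)/0.328 = 0.5719.
- E = 0.6031 + 0.0767×0.8095 + 0.0820×0.5719 = 0.7121. Bias +3.2 points.
- Dropouts who had lost response are imputed on average at (0.02655×0.8095 + 0.0615×0.5719)/0.08805 = 0.64, against a true 0.15. Across all scenarios this imputed value runs from about 0.56 to 0.71.

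**Bias in percentage points, active arm, history through Week 16 only:**

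| Dropout: responders vs non-responders | No ICE 1 | Half ICE 1 | 80% ICE 1 |
|---|---|---|---|
| 15% vs 15% | 0.00 | −1.19 | −1.85 |
| 10% vs 20% | +1.54 | −0.05 | −0.93 |
| 10% vs 30% | +3.22 | +0.67 | −0.68 |
| 10% vs 40% | +5.05 | +1.40 | −0.44 |
| 15% vs 50% | +6.46 | +1.38 | −1.03 |
| 20% vs 60% | +8.17 | +1.33 | −1.72 |
| 20% vs 10% | −1.60 | −2.38 | −2.84 |

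The sign turns negative as the ICE 1 share rises because those non-responses pull down q_R for everyone still missing, including those who were responding when they left.

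**Placebo crossovers**, with Week 16 status assumed uninformative and 0.72 responding at the last visit: at 10% vs 30% dropout the bias is +3.6, +0.8 and −0.8 points with none, half and 80% ICE 1.

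**Adding the last observed response to the model** brings the bias to between −0.6 and 0.0 points in every active-arm scenario above.

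**Simulation check** (400,000 participants, logistic imputation, two intermediate visits, no ICE 1): 0.0, +3.6 and +5.6 points at 15% vs 15%, 10% vs 30% and 10% vs 40%. With full history the estimate was within 0.1 point of the truth.

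**The case against.** The strongest reply is that the literal reading is not the natural one. The model says "PASI 90 response or IGA 0 or 1 response status through Week 16" because its target visit is Week 16, and 4.4.2.4 borrows the method, not the visit. The model cannot be run unchanged anyway: the later responses must enter as variables to be imputed, and fully conditional specification normally predicts each variable from the others. A separate simulation on assumed inputs (60,000 participants per scenario, 59% response at Week 16 and 72% later, 18–23% missing) supports this. With Weeks 64–156 as joint targets, and Weeks 20–52 still omitted, bias was 0.0 to +0.1 points with no ICE 1 and −0.9 to −0.1 with ICE 1. The Week-16-only model gave +1.7 to +4.4 with no ICE 1 and +0.1 to +0.8 with half. This stands as a limit on size. It does not supply the missing specification: on that reading the predictors, visits and treatment coding are unwritten.

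Second, ICE 1 takes out many of the participants of concern, and Protocol 7.1 keeps those who stop treatment in scheduled visits. Both points stand. What remains is loss to follow-up, withdrawn consent, stopping for another recorded reason with later visits missing, and missed visits.

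Third, the stakes are low. SAP 4.4.2 makes no multiplicity adjustment for exploratory endpoints, and observed-case and MMRM analyses sit alongside. That stands for alpha. The observed-case rate is not an independent safeguard, though: in the worked case it is 0.7168 against a true 0.6799, or +3.7 points, so its agreement with the imputed rate would not be reassuring.

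**Conclusion.** The Week 64–156 imputation model is not specified for the period it serves, and followed literally it omits the most informative data collected. That much rests on the text alone.

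A reader might go further and infer that long-term durability is overstated because everyone who had lost response is filled in at the average rate. The documents do not support that. Those who stop for lack of efficacy or worsening psoriasis are counted as non-responders. The imputed value is conditional on Week 16 status, baseline score, arm and strata, and approaches a plain average only for placebo crossovers. The direction depends on quantities that the documents do not give. On the assumptions above, the literal reading gives about +1.5 to +8 points if non-responders leave more often and none are ICE 1, about −0.1 to +1.4 if half of the lost-response dropouts are ICE 1, and as low as −2.8 elsewhere. With history carried to the visit analysed, it is near zero.

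The conflict over observed cases is separate and firm: one section applies no ICE rule and two others apply ICE 1. No confirmatory test is affected. The point is worth settling before the long-term database locks.

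**What to change.** In SAP 4.4.2.4, replace the cross-reference with an FCS model written for Weeks 64–156 that:

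- includes observed responses at all earlier visits up to the analysis week, at least Weeks 16, 24 and 52 and each later visit;
- uses treatment sequence (continued, withdrawn/retreated, not re-randomised, placebo crossover) in place of the Week 0 arm alone;
- names every binary endpoint to be imputed.

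State one observed-case rule, and make 4.4.2.4, 4.4.2.5 and 4.4.2.6 agree with it. Imputing PASI and IGA scores and then deriving response is an option, not a requirement.

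The cost is SAP wording, some extra programming and a longer run. No new data are needed. The long-term rates may change in either direction.
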